## 2.7. Purpose of the Analyses

The main purpose of this study is to evaluate the safety, tolerability (primary objective) and immunogenicity (secondary objective) of NDV-HXP-S vaccine across a range of S-antigen dose levels – one with CpG 1018 as adjuvant – with the aim of expeditiously selecting a single candidate to advance to Phase 3 studies. The proposed dosing regimen for the tested vaccines is to administer two doses with 28-day interval. The period of 28 days between prime and boost was selected because it is the acceptable dosing interval for many licensed vaccines and other COVID-19 vaccines which are being developed. The analysis of data from Phase 1 will provide justification for advancement to the Phase 2 segment based on safety evaluations during an initial sentinel dose-escalation stage, and later an interim analysis of safety and immunogenicity (the latter primarily based on pseudovirus neutralization) through 28 and 14 days after the second dose, respectively.

An independent Data and Safety Monitoring Board (DSMB) will review unblinded safety data through Day 57, and on the basis of this review provide a recommendation for advancing

to Phase 2 (the DSMB will also be convened at any time during conduct of the study in the event that a study pause rule is triggered). In addition to this process for assessing adequate safety for advancing to Phase 2, a threshold immune response at Day 43 will be required for a vaccine formulation to be considered for advancement to Phase 2: namely, the observed seroresponse rate (defined as the percentage of subjects in a treatment group with at least a 4-fold rise from baseline in NT80 titers) will need to be at least 52% at the lower limit (LL) of the 95% confidence interval (CI). Based on this criterion, there is less than 10% chance of incorrectly rejecting a vaccine candidate with a true seroresponse rate of 85% or higher, which is estimated to be the minimum response rate that would be consistent with further investment in an additional second-wave COVID-19 vaccine.

If warranted based on safety and immunogenicity, the two optimal NDV-HXP-S formulations will be selected for ongoing evaluation in Part 2 of the study based on results of the Phase 1 interim analysis. The Phase 2 segment of the study will include a sufficient number of older adults aged 60-75 (including those with stable chronic co-morbidities) to determine whether safety and immunogenicity of the vaccine may differ in this older population. It is critical that evaluation of NDV-HXP-S in older adults informs the selection of the NDV-HXP-S candidate to advance to Phase 3 studies (based on safety and immunogenicity through 14 days post-second vaccination in Phase 2), given the higher risk of severe COVID-19 in this age group, and the potential need for a higher dose level of antigen and/or use of adjuvant to achieve a comparable functional immune response as younger adults. Phase 2 immunogenicity and safety data through Day 43 and Day 57, respectively, will determine the vaccine composition to advance to Phase 3, registration, and commercialization. Cell-mediated immunity will also be evaluated in a subset of subjects in the Phase 2 segment as an exploratory objective to assess the S protein-specific T cell response including Th polarization. An exploratory evaluation of the IgG immune response against the NDV HN protein will also be conducted in all Phase 2 subjects to generate hypotheses about the utility of administering a booster dose of NDV-HXP-S vaccine.

In addition to standard safety monitoring throughout the study, subjects will be evaluated for specific adverse event of special interest (AESI); these include potential immune-mediated medical conditions, which may be associated with vaccination. In addition subjects will be closely monitored for adverse events associated with COVID-19 to identify, and treat if indicated, potential cases of COVID-19 during the trial, and to assess for possible vaccine-induced immune enhancement of disease. In addition to mandatory use of masks and other exposure control measures by staff and subjects during clinic visits, study subjects will be instructed to contact the Principal Investigator (PI) if they meet criteria for COVID-19 testing based on specified signs and symptoms; these criteria will be provided to subjects in the form of a fact sheet.

The ultimate aim of developing NDV-HXP-S vaccine for the prevention of COVID-19 is to obtain local registration of the vaccine in Vietnam, followed by prequalification by the WHO, with the goal of providing affordable access to a life-saving COVID-19 vaccine for Vietnam and other LMICs.

This SAP describes the statistical methodology and summaries required to assess the safety

tolerability and immunogenicity of NDV-HXP-S vaccine across a range of S-antigen dose levels to facilitate the selection of two candidates to advance to Phase 2.

### **3. STUDY OBJECTIVES AND ENDPOINTS – PHASE 1**

The Phase 1 study objectives are listed here as in the protocol.

#### **3.1. Study Hypotheses**

The study will test the hypotheses that the NDV-HXP-S vaccine (NDV-HXP-S) have an acceptable safety profile and be well-tolerated at all dose levels when administered as a two-dose regimen either without adjuvant (at 1 µg, 3 µg, and 10 µg of S protein per 0.5 ml dose), or with the adjuvant CpG 1018 (at 1 µg of S protein per 0.5 ml dose) and to test that NDV-HXP-S elicit a measurable and dose-dependent neutralizing antibody response.

##### **3.1.1. Primary Objective**

###### **Safety and Tolerability**

- To assess the safety and tolerability of each of four formulations of NDV-HXP-S (at 1, 3 and 10 µg without adjuvant; and at 1 µg with CpG 1018) after the first and second dose of a two-dose regimen administered at a 28-day interval to adults aged 18-59 years

##### **3.1.2. Secondary Objectives**

###### **Immunogenicity**

- To assess the functional (neutralizing) humoral immune response elicited by each formulation of NDV-HXP-S, as measured by a SARS CoV-2 pseudovirus-based neutralization assay (PNA), at baseline, 28 days after the first vaccination, and 14 days after the second vaccination (to inform the selection of two formulations for evaluation in Phase 2), and 6 months after the second vaccination
- To assess the Immunoglobulin G (IgG) immune response elicited by each formulation of COVIVAC against the S protein of SARS-CoV-2, as measured by enzyme-linked immunosorbent assay (ELISA), at baseline, 28 days after the first vaccination, and 14 days and 6 months after the second vaccination

##### **3.1.3. Exploratory Objective**

- To assess the Immunoglobulin G (IgG) immune response against NDV HN as measured by enzyme-linked immunosorbent assay (ELISA), at baseline, 28 days after the first vaccination, and 14 days, 6 months after the second vaccination (*note: NDV HN ELISA is under development*)
- To assess the NT80 immune response elicited by each COVIVAC formulation as measured by PNA at baseline, 28 days after the first vaccination, and 14 days and 6 months after the second vaccination

## 3.2. Study Endpoints

### 3.2.1. Primary Endpoints

#### Safety and Tolerability

- Number and severity of solicited local and systemic AEs during the first 7 days after each vaccination
- Number, severity, and relatedness of clinically significant hematological and biochemical measurements at 7 days post each vaccination
- Number, severity and relatedness of all unsolicited AEs during the first 28 days after each vaccination
- Number, severity and relatedness of SAEs throughout the entire study period
- Number, severity and relatedness of MAAEs throughout the entire study period
- Number, severity and relatedness of AESI throughout the entire study period, including AESI relevant to COVID-19, and potential immune-mediated medical conditions (PIMMC)

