**3.3.12. Adverse Event Recording and Reporting**

Recording and reporting of all AEs will occur from signing of the ICF (enrollment) through 28 days post-second injection (Visit 6) for each study subject receiving study product. SAEs, MAAEs, and AESI will be recorded throughout the study period. The Study staff must completely and promptly record each AE in the source documentation and on the AE CRF,

regardless of relationship to the vaccine administered/procedure as determined by the PI/designee. The PI/designee will attempt, if possible, to establish a diagnosis based on the signs and symptoms. When a diagnosis for the reported signs or symptoms is known, the PI/designee will report the diagnosis as the AE, not the signs and symptoms. Adverse events will be classified by MedDRA term and by severity/intensity, relatedness, and outcome.

Enrolled subjects who subsequently screen fail (i.e., who never underwent randomization) will have any AEs recorded from enrollment until the time they are determined to be ineligible for randomization or withdraw consent. These AEs will be listed in separate appendices from those subjects randomized and vaccinated. For the purposes of data capture they will be closed at the point the subject is deemed ineligible.

Reporting of AEs will follow the regulatory guidelines of the Ministry of Health and NIHE's Ethics Committee (EC) in regard to requirements, processes and forms.

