- Recent history (within the past year) or signs of alcohol or substance abuse.
- Any medical, psychiatric or behavior condition that in the opinion of the PI may interfere with the study objectives, pose a risk to the subject, or prevent the subject from completing the study follow- up.
- Employee of any person employed by the Sponsor, the contract research organization (CRO), the PI, study site personnel, or site.

**Note:** specific exclusion criteria (e.g.,  $\geq$  Grade 2 acute illness, or abnormal vital sign deemed clinically relevant by the PI/designee) will be reassessed at both vaccination visits. Any subject who cannot be vaccinated due to an acute abnormality assessed at a vaccination visit (Visit 1 or Visit 3) may return once the acute issue has resolved, if deemed appropriate by the PI/designee. A minimum of 48 hours must have passed after a documented fever before a subject can be vaccinated. This safety requirement will not be deemed a protocol deviation should the visit fall outside the vaccination window; however, it will be encouraged to maintain the vaccination window whenever possible in these situations. Clinical laboratory test results and vital signs used to determine subject eligibility will be those obtained at screening. These tests may be repeated once if deemed appropriate by the investigator and determined to be due to a transient condition that has resolved. In addition, a test may also be repeated for test results determined to be spurious by the investigator (e.g., following improper specimen collection). The last measurement will be taken as the baseline for purposes of analysis.

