### 8.3. Adverse Events

All safety assessment will take place in the safety analysis population, according to the treatment received. All subject-level percentages (solicited/unsolicited AEs, clinical safety laboratory abnormalities, etc.) will be supplemented with two-sided 95% CIs computed via the Clopper-Pearson method. Individual summaries (denominators for percentages) will be limited to the number of subjects with the appropriate analysis population with the data available for analysis for the given endpoint. Summaries will be provided overall by group and by stage ([Table 39](#), [Table 41](#), [Table 42](#), [Table 60](#), [Table 64](#)).

The non-serious adverse events from combined solicited and unsolicited (excluding serious adverse event) that being reported during the first 28 days after each vaccination will be summarized with the number of subject by vaccination groups. This combined data will be summarized by System Organ Class (SOC) and Preferred Term (PT) also ([Table 39](#) and [Table 40](#)).

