### 8.3.2. Unsolicited Adverse Events

Overall number of subject experiencing unsolicited AEs, including SAEs, onset during the first 28 days after each dose vaccination will be summarized by vaccine groups and relatedness ([Table 41](#)). Number of subject experiencing SAEs throughout the entired study period will also be presented ([Table 42](#)). All unsolicited AEs with onset during the first 28 days following each dose administration will be assessed for severity and as either related or not related to study product by the investigator ([Table 43](#) and [Table 44](#)).

AESI, MAAEs, and SAEs: All AESI, MAAEs, and SAEs through Visit 7 (Day 197) will be recorded and the number, severity, and relatedness to study product will be summarized ([Table 45](#) through [Table 49](#)). Subject-wise data listing for all unsolicited AEs will be provided ([Listing 7](#)).

When an AE occurs more than once for a subject, the subject will be counted only once for the corresponding PT according to the maximum severity of the events.

Medically-attended adverse events (MAAEs) are unsolicited AEs for which the subject received medical attention, such as during an emergency room visit or a visit to or from medical personnel (e.g., medical doctor).

Adverse events of special interest (AESIs) for this study include:

- Potential immune-mediated medical condition (PIMMC), given that vaccination has been associated with autoimmunity
- AEs associated with COVID-19, given the importance of subject safety of managing any occurrence of COVID-19, and the possible association of vaccination with enhancement of COVID-19

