with vaccine-related AESIs								
withdrawn due to an AESI								
2nd Dose Vaccination								
with one or more AESIs								
Potential immune-mediated medical conditions (PIMMC)								
Associated with COVID-19								
with no AESI								
with vaccine-related AESIs								
withdrawn due to an AESI								

**Note:** “N” is the total number of subject in each group and “xx” represent the value number.

**Table 42: Overall Number of Subjects with Serious Adverse Events throughout the Entire Study Period in Safety Analysis Population**

	All (N = 120)	COVIVAC				Placebo (N = 20)
		1 µg (N = 25)	3 µg (N = 25)	10 µg (N = 25)	1 µg + CpG (N = 25)	
		n (%) (95% CI*)	n (%) (95% CI*)	n (%) (95% CI*)	n (%) (95% CI*)	
with one or more serious adverse events	xx (xx.x%) (xx.x-xx.x)					
with no serious adverse event						
with vaccine-related serious adverse events						
with medically-attended serious AE (MAAEs)						
with serious adverse events of special interest (AESI)						
Potential immune-mediated medical conditions (PIMMC)						
Associated with COVID-19						
withdrawn due to a serious adverse event						
SAEs leading to death						

**Note:** “N” is the total number of subject in each group and “xx” represent the value number.

**Table 43: Number of Subjects with Serious Adverse Events Onset during the First 28 days after each Vaccination by Severity**

	All (N = 120)	COVIVAC				Placebo (N = 20)
		1 µg (N = 25)	3 µg (N = 25)	10 µg (N = 25)	1 µg + CpG (N = 25)	
1st Dose Vaccination						
with one or more serious adverse events by severity*	xx (xx.x%)	xx (xx.x%)	xx (xx.x%)	xx (xx.x%)	xx (xx.x%)	xx (xx.x%)
Grade1 (Mild)	xx (xx.x%)	xx (xx.x%)	xx (xx.x%)	xx (xx.x%)	xx (xx.x%)	xx (xx.x%)
Grade2 (Moderate)	xx (xx.x%)	xx (xx.x%)	xx (xx.x%)	xx (xx.x%)	xx (xx.x%)	xx (xx.x%)
Grade3 (Severe)	xx (xx.x%)	xx (xx.x%)	xx (xx.x%)	xx (xx.x%)	xx (xx.x%)	xx (xx.x%)
Grade4 (Potentially life-threatening)	xx (xx.x%)	xx (xx.x%)	xx (xx.x%)	xx (xx.x%)	xx (xx.x%)	xx (xx.x%)
with no serious adverse event	xx (xx.x%)	xx (xx.x%)	xx (xx.x%)	xx (xx.x%)	xx (xx.x%)	xx (xx.x%)
with vaccine-related serious adverse events by severity*	xx (xx.x%)	xx (xx.x%)	xx (xx.x%)	xx (xx.x%)	xx (xx.x%)	xx (xx.x%)
Grade1 (Mild)	xx (xx.x%)	xx (xx.x%)	xx (xx.x%)	xx (xx.x%)	xx (xx.x%)	xx (xx.x%)
Grade2 (Moderate)	xx (xx.x%)	xx (xx.x%)	xx (xx.x%)	xx (xx.x%)	xx (xx.x%)	xx (xx.x%)
Grade3 (Severe)	xx (xx.x%)	xx (xx.x%)	xx (xx.x%)	xx (xx.x%)	xx (xx.x%)	xx (xx.x%)

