**Table 59: Summary of Serious Adverse Event by Action Taken to the Study Vaccine throughout the Study Period**

Action Taken to the Study Vaccine	COVIVAC										Placebo (N = 20)	
	All (N = xx)		1 µg (N = 25)		3 µg (N = 25)		10 µg (N = 25)		1 µg + CpG (N = 25)			
	NE	n (%)	NE	n (%)	NE	n (%)	NE	n (%)	NE	n (%)	NE	n (%)
All												
Withdrawn												
Delayed												
Continued												
Not applicable												

**Note:** NE: Number of events

n: Number of subject with at least one AE / %: (n/N)\*100

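### Second-dose AE panels have two conflicting denominators, and non-serious AEs starting outside both 28-day windows reach no AE summary table

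*SAP*

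**What the plan says.** **Counting window.** Section 3.2.1 defines the primary endpoint as "Number, severity and relatedness of all unsolicited AEs during the first 28 days after each vaccination". Section 8.3.2 carries this into Table 41: unsolicited AEs, SAEs included, with "onset during the first 28 days after each dose vaccination will be summarized by vaccine groups and relatedness". Tables 39, 40, 50, 54, 56 and 58 have the same 28-day limit in their titles.

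**Recording period.** Under section 3.3.12, AEs are recorded without a break from consent "through 28 days post-second injection (Visit 6) for each study subject receiving study product".

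**Timing of dose 2.** The visit schedule (Table 3) puts dose 2 at Day 29 (+3). Section 4.2.3 allows deferral after an acute abnormality: "This safety requirement will not be deemed a protocol deviation should the visit fall outside the vaccination window". Section 8.5 stops further product after a pregnancy arising before Visit 3 but encourages the subject to complete the remaining visits. Table 4 has rows for missed and delayed vaccine administration, so both cases are expected.

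**Denominator.** Section 8.3 limits denominators to subjects "with the data available for analysis for the given endpoint", and section 6.3.3 lets them differ by safety endpoint. The notes to Tables 40, 41 and 43 say that N "is the total number of subject in each group", and the Table 50 note says the same of patients. All four tables have second-dose panels under the same column heads as the first-dose panels, with planned sizes of 25 and 20 printed.

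**Interim report.** Section 6.6.1 includes Tables 39-42 and Listings 7-9. It does not include Tables 45-48.

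**The concern.** There are two separate issues.

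The denominator of a second-dose rate should be the subjects who received the second dose. The shells point to the whole group. The body text points to subjects with data, but does not say whether a one-dose subject still in follow-up has data for the second-dose period. Two programmers could produce different percentages and each claim to have followed the SAP. On the shell reading, someone who stopped after dose 1 is reported as having had no adverse event after dose 2. The distortion would grow with an arm's stopping rate, which matters when arms are compared for advancement.

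The window issue is about completeness. Section 4.1 bases down-selection on post-dose safety results that take in all solicited and unsolicited AEs. The summary tables cover two 28-day windows, and those windows meet only if dose 2 is given on schedule.

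**Working it through.** **The plan's own safety figure.** Section 5 gives exact 95% upper bounds of 13.7% (25 subjects) and 2.4% (150 subjects) when no events are seen. The formula is 1 − 0.025^(1/n):
- n = 25: 13.72%
- n = 150: 2.43%

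Both figures reproduce. They assume that everyone counted was at risk.

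**Denominator.** Let m of the 25 in a vaccine arm receive dose 2, and let x of those m report an AE. The rate among recipients is x/m and the shell rate is x/25, so the shell rate equals the recipient rate times m/25. The SAP gives no expected number without a second dose, so m is an assumed range:

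| m | m/25 | relative understatement |
|---|---|---|
| 24 | 0.96 | 4% |
| 23 | 0.92 | 8% |
| 22 | 0.88 | 12% |
| 20 | 0.80 | 20% |

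Illustration with x = 5 and m = 22, Clopper-Pearson intervals:
- shell: 5/25 = 20.0% (6.8 to 40.7)
- recipients: 5/22 = 22.7% (7.8 to 45.4)
- no-adverse-event row: 20/25 = 80.0% against 17/22 = 77.3%
- upper bound with zero events: 13.7% (n = 25) against 15.4% (n = 22)

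If section 8.3 is read as requiring data for the post-dose-2 endpoint specifically, N is already m and the difference is nil.

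**Window.** Dose 1 is on Day 1. The 28-day window ends on Day 29, or on Day 28 if the vaccination day counts as the first of the 28; the SAP does not say which. The gap is the days after that end and before dose 2:

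| Dose 2 | window ends Day 29 | window ends Day 28 |
|---|---|---|
| Day 29 | 0 days | 0 days |
| Day 32 (last day in window) | 2 days | 3 days |
| Day 43 (assumed deferral) | 13 days | 14 days |
| Not given, to nominal Visit 6 (Day 57) | 57 − 29 = 28 days | 57 − 28 = 29 days |

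**Where a gap AE would appear.**
- Non-serious, neither medically attended nor of special interest: Listing 7 only.
- Non-serious MAAE or AESI: Listing 7 and Tables 45-48. Those tables are not in the interim report, so at the interim it is in Listing 7 only.
- Serious: Table 42, which covers the whole study and is in the interim report.

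**The case against.** **The denominator is already dealt with.** Sections 8.3 and 6.3.3 tie denominators to data for the specific endpoint, and the endpoint is defined per vaccination. Someone with no second vaccination has no post-dose-2 period and so no data for it. The printed group sizes are mock values: Table 7 shows 20 in every vaccine arm where other shells show 25. The one written percentage formula, in the Table 59 note (n being "Number of subject with at least one AE", divided by N), belongs to a whole-study table with no dose panels. Much of this stands, and a reader who infers that the SAP plainly divides by all dosed subjects goes too far. What survives is that four shell notes say otherwise. The example in section 6.3.3 is solicited AEs, where a one-dose subject has no second-dose record and drops out naturally. Unsolicited AEs are collected continuously, so that subject arguably does have data. Neither section says that the subject must have received dose 2.

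**Gap AEs are not lost.** Listing 7 covers all unsolicited AEs and is in the interim report. The PSRT sees all new unsolicited AEs, and the DSMB reviews safety data through Day 57 with no 28-day limit stated. This stands, so the gap is one of tabulation only.

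**The 28-day window is the stated endpoint.** This also stands. Replacing it with treatment-period counting would be a preference.

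**No decision is shown to change.** The SAP sets no numerical AE threshold for advancement, and 20.0% against 22.7% lies well within the intervals at this sample size.

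**Conclusion.** Two minor problems of specification hold.

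1. The notes to Tables 40, 41, 43 and 50 conflict with section 8.3 on the denominator of second-dose panels. Any understatement is conditional on the shells being followed: a factor of m/25, or 4% to 20% relative over the assumed range m = 24 to 20. Under section 8.3 applied per dose it is zero.
2. Non-serious unsolicited AEs starting outside both 28-day windows are recorded but enter none of Tables 39-41, 50, 54, 56 or 58. The exposure is 0 to 3 days for in-window dosing. It is longer after a deferral and 28 to 29 days to nominal Visit 6 with no dose 2.

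A reader might infer two stronger things that the SAP does not support. One is that gap AEs pull second-dose rates down. They start before dose 2 or in subjects who never had it, so they are not second-dose events, and events within 28 days after a late dose 2 are still counted. The other is that the AEs behind stopping or deferral are those most likely to be missed. Deferral follows an abnormality assessed at the vaccination visit. With the window ending on Day 29, an illness present at a Day 29 visit began inside the dose-1 window and can enter the delayed row of Table 58. Only later onsets escape, such as Days 30-32 in a subject attending late, or a new illness during a deferral.

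The m values are illustrative. The 22 evaluable subjects in section 5 are an immunogenicity assumption, not a forecast of missed second doses.

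**What to change.** - In section 8.3, state that every second-dose panel (Tables 29-41, 43, 50, 52, 54, 56 and 58, where applicable) uses as N the subjects who received dose 2 and have data for that period. Print that N at the head of the panel.
- Amend the notes to Tables 40, 41, 43 and 50 to agree with section 8.3.
- Keep the 28-day count as the endpoint, and say whether the vaccination day is the first of the 28 days.
- In Tables 39-41, 50, 54, 56 and 58, add a row or column for AEs with onset outside the two windows through Visit 6.

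The AEs are already recorded under section 3.3.12, so no new data are needed. The cost is SAP and shell wording, some programming, one more row or column per table, and denominators that differ between the dose panels. The protocol is not at hand, so whether it needs a matching edit cannot be confirmed.
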